### **Outcome Measure(s)**

The primary outcome, FMC to reperfusion, will be measured using electronic health records from CTEMS and WFUSM. Patient reperfusion times will also be compared to the AHA time goal. Reperfusion times are routinely and reliably documented in both the EMS and hospital electronic health record. Our data team has ample experience collecting these measures in prior clinical trials.

Protocol version:

Template updated 9.24.14

For each STEMI patient in Qualla Boundary, we will obtain their FMC to reperfusion time and their sub-component times (e.g., FMC to EKG time, EKG to activation time, activation to reperfusion [by fibrinolytic or PCI] time) and these will be recorded in a study database. Data will be aggregated from patients before (baseline) and after EMS telehealth STEMI program implementation. FMC to reperfusion time will be reported as a mean with standard deviation and as a median with interquartile range.

- Qualla Boundary has a population greater than 5,000 with a local non-PCI hospital within its locality that serves locals and surrounding communities. Closest PCI centers utilized by CCTEMS are greater than 50 miles and 70 minutes away depending on dispatch location.
- The expected end of the study is defined as the completion of the project, year of 2025. In addition, the Investigator may decide to terminate the study at any time.
- The total length of the study, from screening of the first patient to the end of the study, is expected to be approximately 23 months.

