**Background, Rationale and Context**

STEMI is the most severe type of heart attack and carries a 30-day mortality of nearly 8%. Reperfusion therapy is the mainstay of treatment for STEMI, either by percutaneous coronary intervention (PCI) or fibrinolysis. Delays in reperfusion are associated with negative health outcomes. Specifically, each 30-minute delay in reperfusion corresponds to a 7.5% decrease in 1-year survival. The current body of literature clearly shows that rural EMS agencies often have longer transport times, which makes the 90-minute first medical contact (FMC) to PCI time goal difficult to achieve. Approximately 16% of Americans live more than an hour from a PCI-capable facility, reinforcing the need for timely therapies in rural prehospital settings to decrease heart muscle damage (disability) and mortality. Recently, our team conducted an analysis of a large national EMS database, which showed that FMC to PCI times were longer for patients treated by rural EMS agencies even after these times were adjusted for distance to destination hospital. In addition, our preliminary data for Cherokee Tribal EMS, who serves the Eastern Band of Cherokee Indians on the Qualla Boundary and its surrounding communities, show that **none of their patients who called 9-1-1 for a STEMI received reperfusion within the AHA time goal**. The American College of Cardiology and AHA support prehospital fibrinolysis when timely PCI cannot be performed. Preliminary data from our HRSA project demonstrates the feasibility of using telehealth to guide care for a patient calling 9-1-1 for acute chest pain and suggests successful expansion to patients with acute STEMI. In Europe, telemedicine programs, which connect EMS providers with expert physicians to assist in EKG interpretation, have improved quality of care and decreased healthcare costs. In addition, these European programs have demonstrated that telehealth can improve STEMI reperfusion times in rural settings. However, STEMI telehealth programs have yet to be implemented and tested in the United States.

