**Current Therapies and Unmet Medical Need Related to STEMI Care**

Rural Americans are much less likely than their urban counterparts to receive timely reperfusion. For example, since January 1, 2020 there were 37 patients with a STEMI cared for by Cherokee Tribal EMS (CTEMS), of which none (0% 0/37) received reperfusion within the American Heart Association recommended time goal. These delays in care are associated with excess mortality and high rates of

Protocol version:

Template updated 9.24.14

long-term morbidity from congestive heart failure and recurrent heart attacks. Eliminating this rural disparity is a top public health priority both nationally and locally. STEMI guidelines from the American College of Cardiology and American Heart Association (AHA) recommend reperfusion within 90 minutes of a patient's first-medical-contact (FMC) with emergency medical services (EMS). In most cases, reperfusion is accomplished with percutaneous coronary intervention (PCI; formerly known as angioplasty with stent) at tertiary care hospitals that offer this advanced capability. However, rural patients often live great distances from PCI centers and therefore have less than a 1/8th odds of timely access to PCI compared to their urban counterparts. It has been estimated that at least 16% of Americans live in rural areas over an hour drive away from a PCI-center, which makes achieving PCI within 90-minutes very difficult. For those expected to have delayed PCI, guidelines recommend administration of fibrinolytics ("clot busting medication"). However, despite these recommendations and evidence suggesting fibrinolytic administration can reduce reperfusion times, few rural EMS agencies currently administer fibrinolytics. For example, over the past four years, Cherokee Tribal EMS has never given fibrinolytics.

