### **Objectives**

**Objective 1:** The primary aim is to assess the impact of implementation of an EMS STEMI telehealth program on patient reperfusion times.

We seek to improve consistent achievement of the reperfusion time goals from 0% to over 75% among STEMI patients in the Qualla Boundary. In Y1 we will begin measuring the project's impact on time from FMC to reperfusion. This will be measured using electronic health records from CTEMS and WFUSM and compared to the AHA time goal of reperfusion within 90 minutes. These times are routinely and reliably documented in the health records, and we have experience abstracting them in prior clinical trials. The baseline proportion of STEMI patients meeting the AHA reperfusion time goal in Qualla Boundary is 0%. In Y2 and Y3 we anticipate achieving the AHA time goal for reperfusion in at least 75% of STEMI encounters.

**Objective 2:** Assess program uptake/adoption by Cherokee Tribal EMS paramedics.

Our goal is to establish a successful telehealth connection in 90% of CTEMS STEMI calls. Telehealth communication will be conducted using Pulsara, a HIPAA compliant platform that can connect the EMS agency to a trained Physician 24/7/365 through a video, voice call, or chat. The EMS agency will be trained on the workflow after identification of patients and when to notify a physician for a further

Protocol version:

Template updated 9.24.14

patient evaluation and medication administration support. We will review electronic health records from CTEMS and WFUSM for STEMI calls and determine if a telehealth connection was made.

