### **Subjects selection criteria**

Project participants will receive standard/usual care and will be identified for participation in electronic quality surveillance retrospectively. For patients identified for participation in this project/quality surveillance, minimal risk is expected from participation beyond that encountered in daily clinical practice, as these participants will receive standard care.

- **Inclusion Criteria**

All patients calling 9-1-1 in Qualla Boundary with possible STEMI as determined by the on scene paramedics will be included in the data.

- **Exclusion Criteria**

As this is a Quality Surveillance study, subjects will not be excluded.

- **Sample Size**

Within the Qualla Boundary we estimate 20-25 patients with EMS calls for possible STEMI will be accrued each year. Our estimated sample size that is treated with TNK is 35 total patients.

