## **Use with Percutaneous Coronary Intervention**

In patients with ST segment elevation myocardial infarction, physicians should choose either thrombolysis or percutaneous coronary intervention (PCI) as the primary treatment strategy for reperfusion. Rescue PCI if medically appropriate or subsequent elective PCI may be performed after administration of thrombolytic therapies; however, the optimal use of adjunctive antithrombotic and antiplatelet therapies in this setting is unknown.

Protocol version:

Template updated 9.24.14

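### Does counting fibrinolysis and PCI alike as reperfusion, with no rule for failed lysis, overstate the gain in time and the share within 90 minutes?

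*Protocol*

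**What the plan says.** The Outcome Measure(s) section makes FMC to reperfusion the primary outcome and breaks it into component times, the last being "activation to reperfusion [by fibrinolytic or PCI] time". Objective 1 has the times "compared to the AHA time goal of reperfusion within 90 minutes" and adds an expectation: "In Y2 and Y3 we anticipate achieving the AHA time goal for reperfusion in at least 75% of STEMI encounters".

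On treatment mix, the section on current therapies says that "over the past four years, Cherokee Tribal EMS has never given fibrinolytics", and that 0 of 37 STEMI patients since January 2020 met the goal. The sample size paragraph says "Our estimated sample size that is treated with TNK is 35 total patients", with 20 to 25 possible-STEMI calls a year. On duration: "The total length of the study, from screening of the first patient to the end of the study, is expected to be approximately 23 months".

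The safety text on use with PCI foresees that "Rescue PCI if medically appropriate or subsequent elective PCI may be performed after administration of thrombolytic therapies". It gives no timing rule for the outcome in such patients. The Background, describing long rural transport, says this "makes the 90-minute first medical contact (FMC) to PCI time goal difficult to achieve"; Objective 1 and the section on current therapies word the same goal as FMC to reperfusion.

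**The concern.** The two periods probably record different events. Before implementation this EMS service gave no lysis, so most times should end at PCI. Afterwards most should end at lysis. That is an inference, because the Protocol does not say whether the local non-PCI hospital gave lysis at baseline.

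The change of route is what the programme is meant to achieve and is not a bias. The worry is narrower. A patient whose lysis fails and who then has rescue PCI could be scored as reperfused when the drug was given and counted as meeting the goal. If the outcome were meant to capture restored flow, each such patient would flatter both the time gain and the 90-minute share, in the post period only. Data are abstracted retrospectively, so an unstated stop event could in principle be settled after the times are seen. The two wordings of the 90-minute goal add to the doubt.

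**Working it through.** **1. The Protocol's own figure.** 0/37 = 0%, as stated. The exact 95% interval is 0 to 9.5%.

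**2. Size of the post cohort.** Accrual per year × 23/12:
- 20 × 23/12 = 38.3
- 25 × 23/12 = 47.9

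So N is about 38 to 48, with 43 as the midpoint. The 35 tenecteplase patients are 35/38 = 92.1%, 35/43 = 81.4% or 35/48 = 72.9% of it. This assumes that all 35 fall within the 23 months and that every possible-STEMI call is a STEMI.

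**3. How far the scoring rule can move the share.** Assume all 35 are dosed within 90 minutes and every PCI, primary or rescue, falls outside. With f the fraction of lysed patients who have rescue PCI, the share scored at rescue time is 35 × (1 − f)/N. The Protocol gives no f; 20% and 40% are illustrations.

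| N | f = 0 | f = 20% (28 patients) | f = 40% (21 patients) |
|---|---|---|---|
| 38 | 92.1% | 73.7% | 55.3% |
| 43 | 81.4% | 65.1% | 48.8% |
| 48 | 72.9% | 58.3% | 43.8% |

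Each rescored patient moves the share by 1/48 = 2.1 to 1/38 = 2.6 points. Reaching 75% takes 29/38, 33/43 or 36/48. So 6 rescored patients are tolerable at N = 38 and 2 at N = 43. At N = 48 the share is already below 75% with none.

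**4. Effect on the comparison.** At N = 43 and f = 40%, 21/43 against 0/37 gives a Fisher p of about 2e-7. The direction and detection of the change in proportion do not depend on the rule.

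**5. Size in minutes.** The Protocol gives no distribution of times, so this would have to be invented, and the results would be fragile. For example, a lognormal PCI time with median 130 minutes and log-SD 0.25 puts 7.1% of patients within 90 minutes. The chance of seeing 0/37 is then 0.929^37, about 6.6%. With median 110, 21% fall within 90 minutes and the chance is about 0.02%. I therefore give no figure in minutes.

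**6. Which reading the text supports.** Step 3 describes an error only if the outcome is restored flow. The places that show the meaning are these:
- The Background names PCI and fibrinolysis as the two forms of reperfusion therapy.
- The section on current therapies says giving fibrinolytics can shorten reperfusion times, calls lysis a medical reperfusion treatment, and states the programme's aim as timely reperfusion by either route.
- The section on use with PCI treats lysis or PCI as the primary reperfusion strategy, with rescue PCI coming afterwards.
- The Appendix 3 form has a field for FMC and a field for administration time. No field records signs of restored flow.

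All of these treat reperfusion as a treatment given. The outcome is then FMC to first reperfusion therapy, and the column f = 0 is the correct score whatever happens later.

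**The case for a change.** The strongest argument for a change is that the event ending the primary outcome belongs in the protocol. No section links the form's administration time to the outcome. A rescue PCI time that is never abstracted cannot be recovered by a later analysis plan. Readers of a published percentage would also want to know what it counts. This stands as a point of clarity: the label is missing, and a reader has to assemble the meaning from several sections.

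It does not show a fault in the measure. Rescoring lysed patients at rescue PCI would be lopsided, because a PCI that fails to restore flow would keep its original time, so only one route could fail. Reporting by route is useful description but a poor comparison: no EMS lysis is expected at baseline, and only 38 − 35 = 3 to 48 − 35 = 13 post-period patients would be treated by PCI alone, selected for not having had lysis. Handling of rescue PCI and any sensitivity analysis may reasonably sit in an analysis plan, which is not at hand.

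The 75% crossings also carry less than they seem to. That figure is an expectation for Y2 and Y3, not a success criterion for the whole 23 months, so the denominators in step 3 are not the ones it refers to. The FMC-to-PCI wording occurs in background text about transport distance; the sections that set the outcome and its goal say reperfusion.

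**Conclusion.** No change to the plan follows. The Protocol omits the stop event for each route and the treatment of rescue PCI, but its consistent use of the term and its form point to FMC to first reperfusion therapy, with administration time as the end point for lysis. That is a sound process measure for a programme meant to bring treatment forward, and on it nothing is overstated.

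Under the alternative target the share within 90 minutes would fall by 2.1 to 2.6 points per rescued patient: for instance from 92% to 74% at N = 38, or from 73% to 58% at N = 48, if 20% were rescued. Those figures rest on an assumed rescue fraction, on every lysed patient being dosed within 90 minutes, and on no PCI patient meeting the goal. The comparison with baseline would keep its direction and, at the midpoint N of 43, its significance even at 40% rescue. The differing wordings of the 90-minute goal are a slip in background text and do not alter the outcome.

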### **Analytical Plan**

Results will be analyzed initially using descriptive statistics. We anticipate time data to be non-normally distributed, therefore reperfusion times pre- and post-implementation will be compared using Wilcoxon Rank Sum tests. In addition, a linear regression model will be used to quantify the association between telehealth program implementation and FMC to reperfusion time while adjusting for the patient's demographics (sex, race, age, and ethnicity) and their distance from the tertiary care center. The proportion of patients meeting the AHA time goal will be reported in percentages with associated 95% confidence intervals before and after implementation. These proportions will be compared using a Chi-squared test. In addition, logistic regression models will assess association between telehealth program implementation and meeting AHA time goals while adjusting for potential confounders (as above).

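### The pre-post comparison of reperfusion times can use only STEMI patients who were reperfused, and the program itself changes who is reperfused

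*Protocol*

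**What the plan says.** Under Subjects selection criteria, the protocol takes in every 9-1-1 caller whom the paramedics on scene judge to have possible STEMI, and adds: "As this is a Quality Surveillance study, subjects will not be excluded".

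Under Outcome Measure(s): "The primary outcome, FMC to reperfusion, will be measured using electronic health records from CTEMS and WFUSM". It continues: "For each STEMI patient in Qualla Boundary, we will obtain their FMC to reperfusion time". The list of component times includes "activation to reperfusion [by fibrinolytic or PCI] time", so either treatment ends the interval. For reporting, "FMC to reperfusion time will be reported as a mean with standard deviation and as a median with interquartile range".

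Under Analytical Plan, "reperfusion times pre- and post-implementation will be compared using Wilcoxon Rank Sum tests", and "a linear regression model will be used to quantify the association between telehealth program implementation and FMC to reperfusion time", adjusted for demographics and distance from the tertiary center. The same section compares the proportions of patients meeting the AHA goal before and after implementation.

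The section on current therapies reports a baseline of 0/37 within the goal and says that Cherokee Tribal EMS gave no fibrinolytics over the past four years. Objective 1 sets the aim: "In Y2 and Y3 we anticipate achieving the AHA time goal for reperfusion in at least 75% of STEMI encounters".

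The protocol does not say how a STEMI patient without a reperfusion time enters any of these analyses.

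**The concern.** A time to reperfusion exists only if reperfusion happens. A patient who dies first, or who is managed without PCI or a fibrinolytic, has no value. A rank test on times, a mean, a median and a linear regression then omit that patient, whose result is arguably the worst of all.

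If the omission were rare and alike in both periods, little would follow. Here there is reason to expect it to differ. At baseline PCI was the only reperfusion this EMS service could lead to without another provider, and the PCI centers it uses are more than 50 miles and 70 minutes away. Afterwards an injection in the field also ends the interval. Some patients who would have had no time at baseline will have one under the program. The two sets of times are thus selected by something that happens after entry and that the intervention alters. A difference between them mixes a change in speed with a change in who is counted. What is at stake is the primary outcome of the study.

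**Working it through.** **1. Who should be in the comparison, and who can be.**

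| Element | Where | Patients covered |
|---|---|---|
| Study population | Subjects selection criteria | All possible STEMI, no exclusions |
| Primary outcome | Outcome Measure(s) | Each STEMI patient, a time presumed obtainable |
| Mean/SD, median/IQR | Outcome Measure(s) | Only patients with a time |
| Wilcoxon test, linear model | Analytical Plan | Only patients with a time |

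The third and fourth rows are narrower than the first two, and no stated rule closes the gap.

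**2. Size of the groups.** The protocol gives no power calculation to reproduce. Baseline is 37 patients. Accrual of 20 to 25 per year over about 23 months gives 20 × 23/12 = 38.3 to 25 × 23/12 = 47.9 possible-STEMI patients; the midpoint, 43, is used below.

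**3. How far selection can move the time comparison.** Simulation with 37 patients before and 43 after, 4,000 runs per setting. Assumed, not from the protocol: lognormal times with median 130 minutes and log-SD 0.3; patients who would have had long times are more likely to go without reperfusion (weight proportional to time to the fourth power); and the loss fractions shown. Both tests are Wilcoxon tests, two-sided at 5%. One uses reperfused patients only; the other keeps everyone and ranks the non-reperfused last.

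Identical underlying times in both periods:

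| Not reperfused, pre / post | Median difference, post minus pre, reperfused only | Rejection, reperfused only |
|---|---|---|
| 0% / 0% | about 0 min | 4.4% |
| 20% / 5% | +5.6 min | 12% |
| 30% / 5% | +9.2 min | 22% |
| 5% / 20% | -5.6 min | 13% |
| 10% / 40% | -11.1 min | 29% |

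A positive difference makes the program look slower, a negative one faster.

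Times truly 20% shorter after implementation:

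| Not reperfused, pre / post | Rejection, reperfused only | Rejection, worst rank |
|---|---|---|
| 0% / 0% | 89% | 89% |
| 30% / 5% | 51% | 96% |
| 10% / 40% | 98% | 3% |

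With more loss at baseline, the reperfused-only test hides much of a real gain. With more loss afterwards, it reports a clear gain although many more patients went without reperfusion.

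**4. What the worst-rank test measures.** It responds to failure to reperfuse as well as to speed. With identical underlying times it rejects 18% of the time at 30% / 5% and 30% at 10% / 40%, because the periods then do differ in how many patients are reperfused. It answers a combined question for all patients, not a pure question about minutes.

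**5. Where the shift comes from.** It needs loss to be related to the time the patient would have had. If loss were unrelated to that time, the reperfused-only medians would not shift systematically, though the failures would still go uncounted.

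**The case against.** Several objections have weight.

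*This belongs in an SAP.* Handling of missing values often does, and an SAP may exist. But this is not a measurement that went missing. The primary outcome is undefined for some of the stated population, and Outcome Measure(s) presumes otherwise. The dropping of patients is inferred from the chosen methods and is not stated; that limit stands.

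*The goal proportion does not have this problem.* A reader might infer that non-reperfused patients also leave the denominator there and so flatter the 75% aim. For instance, 17/24 = 71% would become 17/22 = 77%. The documents do not support that reading. The current-therapies section counts 0/37 over all STEMI patients the service cared for, Objective 1 refers to STEMI encounters, and the Analytical Plan refers to patients. A never-reperfused patient most naturally counts as not having met the goal. Nor is 75% a tested threshold: it is anticipated, and the exact 95% intervals for 17/24 (49% to 87%) and 17/22 (55% to 92%) both include it. Against 0/37, Fisher's p is below 1e-8 with either denominator.

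*The bias may run against the program.* A reader might assume that it always flatters. If the main effect is that baseline patients who died in transport are left out, the time comparison understates the benefit. The documents fix neither direction nor size.

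*Deaths before reperfusion may be few.* The background section's figure of nearly 8% is 30-day mortality. It does not give the share who die before reperfusion and cannot be used as a rate here.

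**Conclusion.** The point holds for the time comparison: the Wilcoxon test, the mean and median, and the linear model. As written, these compare patients selected by a post-entry event that the program changes, so a pre-post difference in minutes cannot be attributed to speed alone. More non-reperfused patients at baseline would understate the benefit, and more after implementation would overstate it, provided that the non-reperfused are mostly those who would have had long times. The size cannot be derived, because no non-reperfusion rate is given. The simulated shifts of about 6 to 11 minutes rest on assumed loss fractions that differ between periods by 15 to 30 percentage points; smaller differences would matter less. The point does not extend to the goal proportion, where only the denominator needs to be confirmed.

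**What to change.** In Outcome Measure(s) and Analytical Plan:

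- Keep every confirmed STEMI encounter in both periods. Restrict this to confirmed STEMI: the enrolled population is possible STEMI, and a false activation must not be given the worst rank.
- In the Wilcoxon test, give the worst (longest) rank to patients who die before reperfusion or never receive it.
- Report the median on all confirmed STEMI encounters. It is defined as long as fewer than half are without reperfusion.
- Keep the mean and the linear model among reperfused patients as supportive, labelled as such.
- Report the number never reperfused, with reasons, for each period.
- For the AHA-goal proportion, state that the denominator is all STEMI encounters and that no reperfusion counts as goal not met.

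The cost is a few sentences. The data should come from the same records, although confirmed STEMI needs a definition applied alike in both periods. The post-implementation figures may become slightly less favourable, and the worst-rank result can no longer be read as a pure difference in time.

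### With the stated baseline of 0/37, the planned adjusted logistic regression for meeting the AHA time goal has no finite odds ratio

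*Protocol*

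**What the plan says.** The Analytical Plan compares patients before and after implementation. For the binary goal it plans percentages with 95% confidence intervals, a Chi-squared test and an adjusted model: "logistic regression models will assess association between telehealth program implementation and meeting AHA time goals while adjusting for potential confounders". The confounders are those listed for the linear model of time: sex, race, age, ethnicity and distance from the tertiary care center. No penalised or exact form is named.

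The same protocol already gives the baseline result. The section on current therapies and unmet need counts 37 STEMI patients since 1 January 2020, "of which none (0% 0/37) received reperfusion within the American Heart Association recommended time goal". Objective 1 repeats it: "The baseline proportion of STEMI patients meeting the AHA reperfusion time goal in Qualla Boundary is 0" per cent. The expected result after implementation is in the same objective: "In Y2 and Y3 we anticipate achieving the AHA time goal for reperfusion in at least 75% of STEMI encounters".

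Two further statements suggest that the zero will persist. On drug treatment by the agency: "over the past four years, Cherokee Tribal EMS has never given fibrinolytics". On distance (Outcome Measures): "Closest PCI centers utilized by CCTEMS are greater than 50 miles and 70 minutes away depending on dispatch location".

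**The concern.** When every patient in one group has the same outcome, ordinary logistic regression cannot put a finite odds ratio on the group effect. The likelihood keeps rising as the coefficient grows, and the software stops wherever its iteration limit or tolerance falls. The coefficient, its standard error, the Wald interval and the Wald p-value then say nothing about the data.

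The protocol chose this model while reporting the zero that defeats it. It is the only planned adjusted analysis of the goal in Objective 1. In a pre-post comparison without a concurrent control, adjustment is the analysis's only protection against differences in case mix between the periods. Unless a remedy is fixed beforehand, the team would have to choose one after seeing the data: drop the model, add a constant or change the method. A reader could also meet a Wald p-value near 1 beside a very large effect.

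**Working it through.** **Inputs**
- Baseline: 0 successes in 37 (Current Therapies and Unmet Medical Need). 0/37 = 0%, which agrees with Objective 1.
- Rate after implementation: about 75% (Objective 1).
- Number after implementation: the protocol gives a yearly figure, "Within the Qualla Boundary we estimate 20-25 patients with EMS calls for possible STEMI will be accrued each year", and a study length that "is expected to be approximately 23 months". If all 23 months count as post-implementation and every call is analysed (assumptions), 20 × 23/12 = 38.3 and 25 × 23/12 = 47.9, so about 38 to 48 patients. I use 28/38 (73.7%) and 36/48 (75.0%).

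The protocol gives no power or sample-size calculation for this comparison, so there is no other figure to reproduce.

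**Step 1: why there is no finite estimate.** Let *a* be the intercept, *b* the implementation coefficient, *k* the successes among *n* post-implementation patients. Without covariates the log-likelihood is

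ℓ(a, b) = −37·log(1 + e^a) + k(a + b) − n·log(1 + e^(a+b)).

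Hold a + b fixed and let *b* grow, so that *a* falls. The post-implementation terms do not change, and the baseline term −37·log(1 + e^a) rises towards 0 without reaching it. So ℓ has no maximum at any finite *b*. With covariates, each baseline patient contributes −log(1 + e^(a + x′γ)), and the same argument holds for any γ. Covariates therefore cannot remove the problem, and the success rate after implementation does not matter as long as *k* is above zero.

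**Step 2: the profile log-likelihood for 36/48.** It is −36.196 at b = 2, −28.802 at 4, −27.262 at 6, −27.029 at 8 and −26.997 at 10. The limit is 36·log(36/48) + 12·log(12/48) = −26.992.

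**Step 3: what software prints.**
- One simulated data set, 37 against 38 patients, with covariates: coefficient 12.7 (SE 31) after 10 iterations, 22.7 (SE 4,643) after 20 and 27.7 (SE 56,557) after 25.
- 300 simulated data sets at each size, with sex, race, ethnicity, age and distance drawn at random (assumed distributions): Wald p between 0.987 and 0.999 in every data set, over repeated runs. Median SEs were about 13,000 to 15,500 at n = 38 and about 12,700 at n = 48. The SE depends on where iteration stops and has no meaning.
- A separate simulation of 500 data sets at each of n = 35 and n = 43 gave a finite maximum-likelihood estimate in none.

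**Step 4: what the same counts do support (unadjusted).**

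| Quantity | 0/37 vs 28/38 | 0/37 vs 36/48 |
|---|---|---|
| Likelihood-ratio chi-squared (1 df) | 2 × (49.553 − 21.901) = 55.3 | 2 × (57.919 − 26.992) = 61.9 |
| Likelihood-ratio p | 1e-13 | 4e-15 |
| Profile-likelihood 95% lower limit for the OR | 47 (no upper limit) | 51 (no upper limit) |
| Firth OR | (28.5/10.5)/(0.5/37.5) = 204 | (36.5/12.5)/(0.5/37.5) = 219 |
| Firth profile 95% CI | 25 to about 26,600 | 27 to about 28,450 |
| Risk difference (Newcombe 95% CI) | 73.7% (55.4% to 85.0%) | 75.0% (58.3% to 85.1%) |

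**Step 5: adjusted Firth fits.** In six simulated data sets the odds ratio ran from 86 to 439, lower limits from 11 to 38 and upper limits from 10,905 to 64,214, with p no larger than 7e-9. After one baseline patient in each was changed to a success, ordinary maximum likelihood gave log odds ratios of 4.24 to 5.57 with SEs of 1.11 to 1.29.

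**The case against.** The arithmetic is not in dispute. The case against rests on four points.

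- **The text does not name an estimator.** It does not mention maximum likelihood or a Wald test. Firth and exact methods are also logistic regression, and such detail is often left to a statistical analysis plan. This stands in part: the remedy fits the present wording. But unqualified logistic regression is ordinarily read as maximum likelihood. The issue is also more than absent detail, because the protocol names a model that, so read, fails on the protocol's own figure.
- **The zero is preliminary.** The baseline in the final analysis may extend beyond the 37, and paramedic-identified possible STEMI may be a somewhat different population. The exact upper 95% limit for 0/37 is 9.5%, helicopter transport exists, and the protocol does not say that no hospital gave fibrinolytics. This stands as a condition. The zero is nevertheless the only baseline figure given, and the travel times (which vary with dispatch location) and the agency's record make it plausible that it persists.
- **The consequence is limited.** The primary outcome is time to reperfusion, and the goal is also covered by two proportions and a Chi-squared test. This stands, and it limits the severity. A likelihood-ratio test would also still give a valid p-value and a lower limit.
- **A penalised odds ratio near 200 with an upper limit in the tens of thousands tells little, and the Newcombe difference is unadjusted.** The upper limit is indeed uninformative. The lower limit and p-value are usable, and the risk difference shows the size of the effect on a readable scale.

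The simulated covariates and the 38 to 48 patients are assumptions, but the separation depends on neither.

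**Conclusion.** The concern holds: the adjusted analysis of the goal is wrong as written and should be fixed. With no baseline patient within goal, ordinary logistic regression gives an infinite odds ratio, and its Wald interval and p-value are meaningless, although the unadjusted likelihood-ratio p-value is about 1e-13 or smaller. This rests on two conditions: the analysed baseline has no success, as the protocol states, and the model is fitted by ordinary maximum likelihood. A single baseline success would remove the separation. The Wilcoxon test, the adjusted linear model of time, the two proportions and the Chi-squared test are not affected.

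**What to change.** In the Analytical Plan, state that the adjusted model for meeting the goal will be fitted by Firth penalised logistic regression, with a profile penalised-likelihood confidence interval and p-value. It remains valid if a baseline success does appear. Exact logistic regression is an alternative only if age and distance are grouped, since continuous covariates can leave its conditional distribution degenerate. Report the unadjusted risk difference with a Newcombe 95% interval alongside, because the upper limit of the odds ratio will be very large.

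The cost is one or two sentences, standard software and no new data. The small price is that the penalised odds ratio is shrunk and its interval stays wide.
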